10.3 Day -14 to Day 0 (Screening Evaluations and First Dose)

Informed consent will be obtained prior to the collection of any data and any study-related procedures. Screening evaluations will be obtained. Subjects will undergo a physical, skin, and cushingoid examination, vitals and a review of medical and concomitant medication histories. Echocardiogram, strength testing/dynamometry, and functional testing (100 meter timed test [100M], North Star Ambulatory Assessment [NSAA], 4-stair climb, and time to arise from floor test) will be conducted.

Lab work will include the following:

- Creatine Kinase
- Gamma-glutamyl transferase (GGT)
- Creatinine
- Blood Urea Nitrogen (BUN)
- Glucose
- Serum Cystatin C
- Electrolytes
- Biomarkers blood draw (for plasma and white blood cells)

Once eligibility has been confirmed (including lab results and echocardiogram review), the pharmacy will dispense a 90-day supply of study medication to the research team who will then provide the study medication to the subject's parent/guardian. If eligibility cannot be confirmed on the same day of screening, the study drug may be shipped to the subject and a pharmacist will counsel the parent or guardian via phone. The day study drug treatment is initiated is considered Day 0.

10.4 Week 1 and Month 1 and 2

Subjects will be contacted by research staff via a REDCap survey to review concomitant medications and assess adverse events.

Lab work will include the following:

- Electrolytes

10.5 Month 3

Subjects will return on Month 3 and undergo a physical, skin, and cushingoid examination, vitals. Strength testing/dynamometry, and functional testing (to include 100 meter timed test, North Star Ambulatory Assessment [NSAA], 4-stair climb, and time to arise from floor test) will

be conducted. Research staff will also review concomitant medications, updates to the medical history, and assess adverse events.

Lab work will include the following:

- Gamma-glutamyl transferase (GGT)
- Creatinine
- Blood Urea Nitrogen (BUN)
- Glucose
- Cystatin C
- Electrolytes

The pharmacy will dispense the supply of study medication to the research team who will then provide the study medication to the subject's parent/guardian. If lab results return after the subject leaves the clinic and the Study Doctor wants additional tests, they will be immediately contacted.

10.6 Month 4 and 5

Subjects will be contacted by research staff via a REDCap survey to review concomitant medications and assess adverse events.

Lab work will include the following:

- Electrolytes

10.7 Month 6 (Final Visit)

Subjects will undergo a physical, skin, and cushingoid examination, vitals and a review of medical and concomitant medication histories. Echocardiogram, strength testing/dynamometry, and functional testing (to include 100 meter timed test [100M], North Star Ambulatory Assessment [NSAA], 4-stair climb and time to arise from floor test) will be conducted.

Lab work will include the following:

- Creatine Kinase
- Gamma-glutamyl transferase (GGT)
- Creatinine
- Blood Urea Nitrogen (BUN)
- Glucose
- Cystatin C
- Electrolytes
- Biomarkers blood draw (for plasma and white blood cells)

Research staff will review concomitant medications, updates to the medical history, and assess adverse events.

10.7.1 Long Term Monitoring

All adverse events occurring throughout the subject's participation in the trial through 30 days after the subject's final study visit will be documented and followed until resolution or stabilization. Research staff will contact subjects 30 days after the subject's final study visit to check for any new AEs and to obtain any new information regarding ongoing AEs.

10.8 Concomitant Medications

Prescribed and over the counter medications used in the 2 weeks prior to trial initiation will be recorded at the screening visit and changes in these medications will be recorded during each subsequent medical history review. The Principal Investigator will encourage subjects to maintain the medication and supplements they are on at enrollment through the course of the trial.

10.8.1 Prohibited Medications

Concomitant use of any of the following medications is prohibited:

- ACEi
- Potassium supplementation

11. ASSESSMENT OF SAFETY

One of the primary objectives for this pilot clinical trial is safety. Withdrawal criteria are based on the development of unacceptable toxicity, as described in section 8.5.

11.1 Adverse and Serious Adverse Events

11.1.1 Definition of Adverse Events

All Adverse Events (AE) will be reported to the Reviewing IRB at annual continuing reviews.

AEs will be collected throughout the trial from informed consent to 30 days after the subject's final study visit. All AEs that occur after any subject has been enrolled, before treatment, during treatment, or within 30 days after the last study visit, whether or not they are related to the study, must be recorded in the eCRF.

Adverse Event: Adverse event means any untoward medical occurrence associated with the use of a drug in humans, whether or not considered drug related.

Adverse events will be graded by the investigator and as used in the CTCAE v.4.03 accordingly:

1. Mild
2. Moderate
3. Severe
4. Life threatening or debilitating
5. Fatal.

Adverse Reaction: An adverse reaction means any adverse event caused by a drug. Adverse reactions are a subset of all suspected adverse reactions for which there is reason to conclude that the drug caused the event.

Suspected Adverse Reaction (21 CFR 312.32(a)): A suspected adverse reaction means any adverse event for which there is a reasonable possibility that the drug caused the adverse event. ‘Reasonable possibility’ means there is evidence to suggest a causal relationship between the drug and the adverse event. A suspected adverse reaction implies a lesser degree of certainty about causality than adverse reaction, which means any adverse event caused by a drug. Suspected adverse events will be reported to the Reviewing IRB at study closeout.

11.1.2 Unexpected Adverse Events (UAE)

Unexpected adverse events are those which are not previously reported with the subject's underlying disease or with the procedures to be used in this trial, or are related to a known toxicity but differ because of greater severity or specificity.

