9.3.1 Risks Associated with Spironolactone

Common side effects associated with the use of spironolactone in this subject population may include: diarrhea, cramping, nausea, vomiting, somnolence, headache, ataxia, gynecomastia and urticaria.

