11.3.2 Safety Reporting

All serious adverse events that are **unexpected** and **possibly, probably, or definitely related** to the use of either study drug should be reported to the Sponsor-Investigator within **48 hours** of the Principal Investigator's initial receipt of the information. All other serious adverse events

should be reported to the Sponsor-Investigator within **7 days** of the Principal Investigator's initial receipt of the information.

The Sponsor-Investigator will report serious adverse events that are unexpected and possibly, probably, or definitely related to the use of either study drug to the Reviewing IRB according to regulatory requirements described as follows:

Any serious adverse event that is fatal or life-threatening, that is unexpected and related to the use of either study drug will be reported to the Reviewing IRB as soon as possible, but not later than **3 business days** after the Sponsor-Investigator's initial receipt of the information.

Serious adverse events that are unexpected and related to the use of either study drug, but are not fatal or life-threatening, will be reported to the Reviewing IRB as soon as possible, but not later than **3 business days** after the Sponsor-Investigator's initial receipt of the information.

If, after further evaluation, an unexpected serious adverse event initially considered not to be related to the use of either study drug is subsequently determined to be related, then the event will be reported to the Sponsor-Investigator within **48 hours** of the determination. The Sponsor-Investigator will report to the Reviewing IRB within **3 business days** of the Sponsor-Investigator learning of the determination.

Relevant additional clinical and laboratory data will become available following the initial serious adverse event report. Principal Investigators must report follow-up information to the Sponsor-Investigator within **48 hours** of initial receipt of the information. All follow-up information relevant to a serious adverse event that is unexpected and related to the use of either study drug will be reported to the Reviewing IRB within **3 business days** of the Sponsor-Investigator's initial receipt of the information.

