11.4 Study Discontinuation Rules

An independent Clinical Safety Monitor will monitor safety data on a continual basis throughout the trial. The Clinical Safety Monitor can recommend early termination of the trial for reasons of safety. Study enrollment will be halted by the Principal Investigators when any subject experiences a Grade 3 or higher adverse event toxicity that is unanticipated and possibly, probably, or definitely related to the study drug that presents with clinical symptoms and requires medical treatment. This will include any subject death, hospitalization, or important clinical laboratory finding. If after review by the Clinical Safety Monitor and the Reviewing IRB, the decision is made to continue, the trial will proceed according to Section 10 of this protocol.

Anticipated adverse events related to progression of Duchenne muscular dystrophy may include muscle weakness, elevated creatine kinase levels, loss of ambulation, scoliosis, short stature, and intellectual disability.

Anticipated adverse events related to prednisolone treatment, which is the standard of care, may include weight gain, cushingoid features, long bone fractures, acne, behavioral disturbance, and short stature (see section 9.3.2 for additional potential side effects).

Anticipated adverse events related to spironolactone treatment may include increased potassium levels, increased breast tissue mass, diarrhea, cramping, nausea, vomiting, headache, sleepiness, unsteadiness, and urticaria (see section 9.3.1 for additional potential side effects).

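### As 11.1.2 is written, a serious weakness or loss of ambulation judged related to spironolactone counts as expected because DMD also causes it, and so misses the faster reporting route in 11.3.2

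*Combined protocol and SAP*

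**What the plan says.** Section 11.1.2 has two limbs. The first sets the reference: "Unexpected adverse events are those which are not previously reported with the subject's underlying disease or with the procedures to be used in this trial". The second adds events that "are related to a known toxicity but differ because of greater severity or specificity". The two limbs meet in the words "underlying disease or with the procedures to be used in this trial, or are related to a known toxicity". Neither limb names a study drug or points to the risk lists in 9.3 or 11.4.

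Section 11.3.2 uses the term to set reporting times. An event that is serious, unexpected and at least possibly related to either drug goes from site to sponsor within 48 hours, then from sponsor to the Reviewing IRB within 3 business days. That covers fatal and life-threatening events and also "Serious adverse events that are unexpected and related to the use of either study drug, but are not fatal or life-threatening". Every other serious event has 7 days from site to sponsor. The Clinical Safety Monitor hears of all serious events within 48 hours of the sponsor's receipt.

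Section 11.4 uses another word, *unanticipated*, in the rule that halts enrolment. It gives three lists of anticipated events, one per cause. The DMD list "may include muscle weakness, elevated creatine kinase levels, loss of ambulation, scoliosis, short stature, and intellectual disability". The spironolactone list reads: "Anticipated adverse events related to spironolactone treatment may include increased potassium levels, increased breast tissue mass, diarrhea, cramping, nausea, vomiting, headache, sleepiness, unsteadiness, and urticaria". Section 9.3.1 lists "diarrhea, cramping, nausea, vomiting, somnolence, headache, ataxia, gynecomastia and urticaria" for spironolactone. Section 9.3.2 names steroid myopathy and muscle weakness for prednisolone.

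**The concern.** Once an event has been judged related to a drug, the useful question for expedited reporting is whether it is already known for that drug. Section 11.1.2 asks mainly whether it is known for the disease. In the spironolactone arm the two questions give different answers for the events that matter most to motor function.

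Spironolactone's effect on motor function is the trial's open question. Section 5.1 accepts that assignment to it may delay prednisolone by up to 6 months, and section 11 calls safety one of the primary objectives. A serious motor decline that an investigator attributes to spironolactone should not take the slower route only because DMD also produces motor decline.

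**Working it through.** No sample size, power or event count enters this point. The check applies the definition to two events in each arm and follows the result through the reporting rules.

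**Can such an event be serious?** Yes. Section 11.1.3 equates Grades 3 to 5 with serious and also counts significant incapacity.

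**Is it unexpected under 11.1.2?**

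| Event, judged drug-related | Listed for DMD (11.4)? | Listed for the drug (9.3, 11.4)? | Result under 11.1.2 | Result against the drug's own list |
|---|---|---|---|---|
| Weakness, spironolactone | Yes | No | Expected | Unexpected |
| Loss of ambulation, spironolactone | Yes | No | Expected | Unexpected |
| Ordinary weakness, prednisolone | Yes | Yes | Expected | Expected |
| Weakness of greater severity, possibly to loss of ambulation, prednisolone | Yes | As weakness only | Can be unexpected (second limb) | Can be unexpected |

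The second limb does not clearly rescue the two spironolactone rows. It needs a known toxicity to start from, and neither spironolactone list has weakness. Ataxia (9.3.1) and unsteadiness (11.4) are the nearest entries.

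Reading the drug as one of the trial procedures does not help either. Section 9.3 separates risks of the study agent from risks of study procedures, and 11.2 grades relatedness to each separately. Even on that reading, an earlier report with the disease would by itself make the event expected under the first limb.

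**What changes in time?** All limits are from 11.3.2, counted from site awareness.

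- Site to sponsor: 48 hours if unexpected and related; 7 days otherwise. Difference: 7 − 2 = 5 days.
- Latest notice to the Clinical Safety Monitor, if unexpected and related: 48 h + 48 h = 96 h = 4 days.
- Latest notice to the Clinical Safety Monitor, otherwise: 7 days + 48 h = 9 days.
- IRB, if unexpected and related: 48 hours, then at most 3 business days after sponsor receipt.
- IRB, otherwise: no report required under that rule. Section 11.1.1 leaves annual continuing review for all adverse events and study closeout for suspected ones.

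**Does the enrolment halt apply?** Section 11.4 never refers to 11.1.2. If an event judged related to spironolactone is checked against the spironolactone list, loss of ambulation is unanticipated. At Grade 3 or higher, with symptoms and a need for treatment, it could then halt enrolment. If it is enough that the event appears on any of the three lists, it is anticipated. The text does not say which reading applies. On the first, the same event is unanticipated for the halt and expected for IRB reporting.

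**A related conflict.** Section 11.3.1 describes IRB reporting of unexpected events related to the corticosteroid product, whereas 11.3.2 says either study drug. Taken alone, 11.3.1 would leave spironolactone out of that sentence.

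**The case against.** The best case on the other side is that other safeguards cover the gap. Much of it stands, and it rules out several stronger conclusions that a reader might draw.

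- *The IRB would never hear of the event.* Not supported. Annual review and closeout remain. Section 11.3.2 also sends information that points to a new or increased risk to the sponsor within 48 hours and to the IRB within 3 business days, with no test of expectedness. Section 18.2 requires prompt reporting of unanticipated problems involving risk. Serious weakening attributed to spironolactone is a plausible candidate for the new-risk route. If it qualifies, these time limits match those of the unexpected-and-related route. But qualifying depends on IRB policy and judgement.
- *Safety oversight is bypassed.* Not supported. Every serious event reaches the sponsor and then the Clinical Safety Monitor, who also receives monthly listings (12.1.1) and can recommend termination. What is lost is speed.
- *The halt cannot be triggered.* Not supported, because the lists in 11.4 are split by cause. The position is unclear, not negative.
- *Both arms are affected alike.* Not supported, because weakness is already a listed prednisolone effect.
- *Known spironolactone effects such as gynecomastia become unexpected.* The first limb alone would suggest this. But the second limb implies that a known toxicity of ordinary severity is expected; otherwise it would add nothing. This is loose drafting, not a firm contradiction.
- *The definition hides a failure of spironolactone to protect muscle.* Lack of efficacy is settled when relatedness is judged, and rewording expectedness would not change that. Motor function is also tested in every boy at Months 3 and 6.

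None of this repairs the specific rule in 11.3.2, which still sorts drug-related events by a definition built on the disease.

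**Conclusion.** The point holds for spironolactone, in this limited form. A serious muscle weakness or loss of ambulation judged related to spironolactone is expected under 11.1.2 as written. The site-to-sponsor limit becomes 7 days instead of 48 hours, the latest notice to the Clinical Safety Monitor 9 days instead of 4, and the specific 3-business-day IRB report is not required. Whether enrolment would be halted cannot be settled from the text.

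This assumes that the investigator judges the event at least possibly related to spironolactone, that the site uses the full time allowed, that 11.1.2 is applied literally, and that the event is not reported as new risk information. The documents give no basis for saying how often this would occur among 24 boys. It is a rule to correct before it is needed.

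**What to change.** For the reporting rules in 11.3, amend 11.1.2 along these lines: an adverse event is unexpected if its nature, severity or specificity is not consistent with the risks listed for the boy's assigned study drug (9.3.1 or 9.3.2, and the drug-specific list in 11.4); known occurrence in DMD is weighed when relatedness is judged, not expectedness.

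Add one sentence on how *unexpected* in 11.3 relates to *anticipated* and *unanticipated* in 8.5 and 11.4. The sponsor should then reconcile 8.5, 11.1.2, 11.3.2 and 11.4, and align the IRB sentence in 11.3.1 with the reference to either drug in 11.3.2. The terms in 8.5 and 11.4 also govern holding of drug, withdrawal and the halt of enrolment. What those rules should be is for the sponsor to decide and is not proposed here.

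The cost is one paragraph in an amendment and a few more expedited reports among 24 boys. Ordinary weakness on prednisolone would stay expected, so that arm should add few.

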11.1.3 Serious Adverse Event (SAE)

An adverse event or suspected adverse reaction is considered “serious” if, in the view of either the Sponsor-Investigator or Principal Investigator, it results in any of the following outcomes: death, a life-threatening adverse event, inpatient hospitalization or prolongation of existing hospitalization, a persistent or significant incapacity or substantial disruption of the ability to conduct normal life functions, or a congenital anomaly/birth defect. Important medical events that may not result in death, be life-threatening, or require hospitalization may be considered serious when, based upon appropriate medical judgment, they may jeopardize the subject and may require medical or surgical intervention to prevent one of the outcomes listed in this definition. Examples of such medical events include allergic bronchospasm requiring intensive treatment in an emergency room or at home, blood dyscrasias or convulsions that do not result in inpatient hospitalization, or the development of drug dependency or drug abuse. **A serious adverse events refers to a grade of 3, 4, or 5.**

All SAEs that occur after any subject has signed informed consent, before treatment, during treatment or within 30 days following the last study visit, whether or not they are related to the trial must be recorded.

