11.3 Time Period and Frequency for Event Assessment and Follow-Up

11.3.1 Obligations of the Principal Investigator

All serious adverse events should be reported to the Sponsor-Investigator regardless of severity, relatedness, or expectedness. The Principal Investigator will provide an electronic report to the Sponsor-Investigator who will report to the Reviewing IRB on any serious adverse event that is both unexpected and related to the use of the corticosteroid product (i.e. there is reasonable possibility that the event may have been caused by the use of the product; the Principal Investigator will not await definitive proof of association before reporting such events).

The Principal Investigator will adhere to any other serious adverse event reporting requirements in accordance with federal regulations, state laws, and the local institutional policies and procedures, as applicable.

The Principal Investigator will be responsible for ensuring that the reporting requirements are fulfilled and will be held accountable for any reporting lapses.

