If a serious adverse event occurs within 30 days after a subject's final study visit and is determined to be unexpected and related to the use of either study drug, that event will be reported to the Reviewing IRB within **3 business days** of the Sponsor-Investigator learning of the determination.

Should a serious adverse event deemed possibly, probably or definitely related to the study agent occur during administration, the study agent will be discontinued, appropriate treatment will be given under medical supervision and the subject will be examined as frequently as necessary thereafter until symptoms cease or stabilize.

All new information and significant noncompliance indicating a new or increased risk or new safety issue as defined in the Reviewing IRB policies will be reported to the Sponsor-

Investigator within **48 hours** of the Principal Investigator learning of the information. The Sponsor-Investigator will report to the Reviewing IRB within **3 business days** of the Sponsor-Investigator's initial receipt of the information. This includes deviations from the protocol that harmed subjects or others or that indicates subjects or others might be at an increased risk of harm.

The Sponsor-Investigator will inform the Clinical Safety Monitor of all serious adverse events regardless of severity, relatedness, or expectedness and of all instances of significant non-compliance impacting patient safety within **48 hours** of the Sponsor-Investigator's initial receipt of the information.

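### Section 11.1.3 defines a serious adverse event by outcome and then by severity grade, so sites can classify the same event differently

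*Combined protocol and SAP*

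**What the plan says.** Section 11.1.3 calls an event serious if "it results in any of the following outcomes: death, a life-threatening adverse event, inpatient hospitalization or prolongation of existing hospitalization", and continues the list with incapacity and congenital anomaly. A further clause covers important medical events, which "may be considered serious when, based upon appropriate medical judgment, they may jeopardize the subject". Neither part mentions grade.

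The same paragraph closes in bold: "A serious adverse events refers to a grade of 3, 4, or 5".

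Grade is defined in Section 11.1.1: "Adverse events will be graded by the investigator and as used in the CTCAE v.4.03 accordingly". The five labels run from mild (1) and moderate (2) through severe (3) to life threatening or debilitating (4) and fatal (5). This is a severity scale.

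Two reporting rules treat severity as something apart from seriousness. Section 11.3.1 states: "All serious adverse events should be reported to the Sponsor-Investigator regardless of severity, relatedness, or expectedness". Section 11.3.2 has the Sponsor-Investigator "inform the Clinical Safety Monitor of all serious adverse events regardless of severity, relatedness, or expectedness".

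Section 11.3.2 also ties a treatment rule to SAE status: "Should a serious adverse event deemed possibly, probably or definitely related to the study agent occur during administration, the study agent will be discontinued".

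**The concern.** Severity describes how intense an event is; seriousness describes what it led to. Section 11.1.3 defines seriousness by the second and then restates it in terms of the first, without saying how the two fit together. A site that works from the bold sentence and a site that works from the outcome list can both believe they are following the protocol and still label the same event differently.

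Several steps depend on the label:

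- the site's report to the Sponsor-Investigator, within 48 hours if the SAE is unexpected and related and within 7 days otherwise (Section 11.3.2);
- the Sponsor-Investigator's notice to the Clinical Safety Monitor within 48 hours, and to the Reviewing IRB within 3 business days for unexpected related SAEs (Section 11.3.2);
- the SAE listing and timeline in the monthly report to the Clinical Safety Monitor (Section 12.1.1);
- discontinuation of the study agent after a related SAE (Section 11.3.2).

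With four to seven centers and grading left to each investigator, any of these can be missed or wrongly triggered.

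**Working it through.** No arithmetic applies; the check is a cross-classification. The inputs are the outcome and important-medical-event definition and the bold sentence (both Section 11.1.3), and the grade labels (Section 11.1.1). The outcome definition is compared with three possible meanings of the bold sentence.

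| Event | Outcome definition alone | Sentence equates (SAE = Grade 3-5) | Sentence adds (outcome OR Grade 3-5) | Sentence restricts (outcome AND Grade 3-5) |
|---|---|---|---|---|
| Grade 1-2, listed outcome such as hospitalization | SAE | not SAE: missed | SAE | not SAE: missed |
| Grade 1-2, no listed outcome, not an important medical event | not SAE | not SAE | not SAE | not SAE |
| Grade 3, no listed outcome, not an important medical event | not SAE | SAE: over-counted | SAE: over-counted | not SAE |
| Grade 3, listed outcome | SAE | SAE | SAE | SAE |
| Grade 4 life threatening, or Grade 5 | SAE | SAE | SAE | SAE |

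Every meaning departs from the outcome definition in at least one row. The literal wording, in which an SAE refers to certain grades, is closest to equating the two, and that is the only meaning that gives errors in both directions.

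**Does another section settle it?** No. Sections 11.3.1 and 11.3.2 ask for SAE reports whatever the severity. That fits the outcome definition better than a definition that fixes a minimum severity, but it does not say what the bold sentence is for.

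**Effect on the treatment rules.** Take an anticipated Grade 3 event related to prednisolone, with no listed outcome and not an important medical event.

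1. Section 8.5 keeps boys with anticipated prednisolone-related events of Grade 1 or higher in the trial.
2. By the outcome definition this event is not an SAE, so the discontinuation rule in Section 11.3.2 does not apply and there is no conflict.
3. Under the equating or adding meaning it is an SAE, so the Section 11.3.2 rule applies when it occurs during administration, while Section 8.5 points the other way.

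The bold sentence therefore widens the overlap between the two rules. Some overlap exists without it, because an anticipated prednisolone-related event that does have a listed outcome meets both rules under the outcome definition.

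**What does not depend on the sentence.** The enrollment halt in Section 11.4 is written directly on grade. Section 13 tests the 100-meter change and gives a sample size that uses no SAE input.

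**The case against.** The strongest reply is that the outcome definition stands on its own and nothing cancels it. On that view the bold sentence adds a criterion, hospitalized Grade 2 events remain SAEs, and the only effect is cautious over-reporting of Grade 3 events. This is a possible reading, and it is why error in both directions cannot be claimed without condition. But the text does not say that the sentence only adds, and even then the over-count brings more events under the discontinuation rule.

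Other points stand in part:

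- Grades 3, 4 and 5 are three severities, so reporting whatever the severity keeps some meaning under the grade reading. The tension is real but is not proof by itself.
- A mislabelled event does not vanish. All adverse events go into the eCRF (Section 11.1.1), the Clinical Safety Monitor receives adverse event details by subject each month (Sections 12.1 and 12.1.1), and the study monitor checks SAE reporting (Section 15.1). What can be lost is the expedited clock.
- Whether a particular admitted boy could be graded 2 depends on CTCAE criteria that the protocol does not reproduce. The protocol's short labels do not rule it out.
- Section 8.5 speaks of staying in the trial and Section 11.3.2 of stopping the agent, so a boy could in principle stay in follow-up off drug. The protocol does not say that this is intended.

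A reader might infer that a comparison of SAE rates between arms is compromised, and note that one reclassified boy moves an arm by 1/12 = 8.3 percentage points. The documents do not support that as the harm. Section 13 plans no by-arm SAE test, Section 12.1.1 asks for SAE listings by subject, and the 8.3 points hold for any yes/no event in an arm of 12 without showing how often grade and outcome would disagree.

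**Conclusion.** The definition is wrong as written and should be corrected. Under each of the three meanings it misclassifies at least one kind of event relative to the outcome definition in the same paragraph: both missed and over-counted events if it equates, over-counted only if it adds, missed only if it restricts. The claim of error in both directions rests on the equating meaning.

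The harm is to safety reporting: inconsistent SAE labels across sites, expedited reports missed or sent needlessly, and unclear application of the discontinuation rule. Its frequency cannot be estimated from the documents. Section 6.3 lists safety as exploratory, while the opening of Section 11 calls it one of the primary objectives; the defect matters under either description. The efficacy conclusions do not depend on it.

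**What to change.** 1. Delete the bold sentence in Section 11.1.3, so that the outcome list and the important-medical-event clause are the only test of seriousness.
2. State that CTCAE grade and seriousness are recorded as separate items. The eCRF is not among the documents, so this may already be the case.
3. If expedited notice of Grade 3 or higher events is wanted, list them as a separate severe-adverse-event category with its own reporting time.
4. Reconcile Sections 8.5, 11.1.3 and 11.3.2 so that a site can tell which rule governs an anticipated prednisolone-related event that is also an SAE. Deleting the sentence narrows this overlap but does not remove it. Which clinical rule should apply is for the sponsor and the clinicians; no view is taken here.

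Cost: a short protocol amendment with IRB approval, notice to the sites, and at most one eCRF field. The definitional change adds no visits or procedures, although it does alter which events fall under the Section 11.3.2 rule.
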